## Diarrhea

Memorial Sloan Kettering Cancer Center  
 [name]  
 [name]

Table 7. Dose modification and management for diarrhea.

Grade	Recommendation
Grade 1	No dose adjustment is required.
Grade 2	Initiate or intensify appropriate medical therapy and monitor as clinically indicated. Interrupt alpelisib dose until recovery to Grade $\leq$ 1, then resume at same dose level.
Grade 3 and 4	Initiate or intensify appropriate medical therapy and monitor as clinically indicated. Interrupt alpelisib dose until recovery to Grade $\leq$ 1, then resume at the next lower dose level.

### Other toxicities

Table 8. Dose modification and management for other toxicities (excluding hyperglycemia, rash, and diarrhea).

Grade	Recommendation
Grade 1 or 2	No dose adjustment is required. Initiate appropriate medical therapy and monitor as clinically indicated. 
Grade 3	Interrupt dose until recovery to Grade $\leq$ 1, then resume at the next lower dose level.
Grade 4	Permanently discontinue alpelisib.

For Grade 2 and 3 pancreatitis, interrupt alpelisib dose until recovery to Grade  $<$  2 and resume at next lower dose level. Only one dose reduction is permitted. If toxicity reoccurs, permanently discontinue alpelisib treatment.

For Grade 2 total bilirubin elevation, interrupt alpelisib dose until recovery to Grade  $\leq$  1 and resume at the same dose if resolved in  $\leq$  14 days or resume at the next lower dose level if resolved in  $>$  14 days.

### Fulvestrant or AIs

There is no dose modification for fulvestrant or AIs

### Benralizumab

The starting dose of benralizumab is 30 mg on the first week of administration as a single dose.

## 11.0 EVALUATION DURING TREATMENT/INTERVENTION

Patients will be seen on day -1 of treatment initiation, day 14, and day 28 with a +/- 7 day window. Each evaluation will consist of the following:

- History and dermatologic examination with standardized photography, ECOG performance status.
- Recording of the adverse events
- Labs, skin tape strips per Table 8

Patients will be assessed radiographically per standard of care.

The PRO-CTCAE, FACT, and allergy questionnaire (Block 2014 FFQ) will be administered at baseline and every 2 weeks (Appendices 2- 4). The allergy questionnaire will be administered at baseline.

All visits will be conducted within the Breast Medicine Service. Any patients with active rash at the time of their study visit should also be evaluated for the rash by the dermatology service for CTCAE grading, photography, and management. If a patient does not have a rash, baseline photography will not be performed; documentation will reflect the absence of a baseline rash.

Table 9 Study Procedures.

Study Procedures	Screening with 14 days of D - 1	Day - 1 to - 7	Day 1 Alpelisib initiation	Day 14±7	Day 28±7	Day 90 (Safety Visit)	Day 365 (Follow Up)
Informed consent	X						
Demographics	X						
Medical history	X						
ECOG	X			X	X		
Skin exam	X			X	X	X	
Vital signs	X			X	X	X	
Comeds	X			X	X	X	
Study Questionnaires	X			X	X	X	
AE evaluation	X			X	X	X	
Skin tape strips	X			X	X		
CBC with Differential/chemistry	X			X	X		
IgE (serum total)	X			X	X		
Allergy Panel	X						
Hyperglycemia panel	X			X	X		
Skin biopsy				X 	X 		
Cytokine panel	X			X	X		
Benralizumab injection		X					
Alpelisib			Once a day by mouth				
Chart Review							X

Allergy questionnaire on Day 1 only; Skin tape strips will be sent to National Jewish Health for analysis CBC with differential and comprehensive metabolic panel. Includes Allergy Aminal, Dust, food screening, grass profile, mold, tree and weed profile. HbA1c, fructosamine, C-peptide (fasting) For patients with rash, a SOC skin biopsy will be conducted and an additional sample sent to National Jewish Health for research analysis. Cytokine panel is to be sent to the sent to immune monitor facility- [name] lab.

## 12.0 CRITERIA FOR REMOVAL FROM STUDY

- 1) > 2 consecutive weeks of a delay in treatment due to toxicities
- 2) Progressive disease (breast cancer)
- 3) Unacceptable toxicity
- 4) Intercurrent, non-cancer related illness that prevents continuation of protocol therapy or follow-up
- 5) Major protocol violation that would render the patient inevaluable for efficacy
- 6) Repeated non-compliance by the patient with protocol requirements
- 7) Changes in the patient's condition or study intervention related toxicity such that, in the opinion of the investigator, continued participation in the protocol would compromise patient well-being
- 8) Withdrawal of patient's consent for personal reasons
- 9) Death

We do not expect any of the above criteria to occur with high frequency as the 4 week PFS for this population is over 90%. All participants for whom we are able to obtain the 4 week primary endpoint (had rash event prior to 4 weeks) will be considered evaluable for the primary rash endpoint under the intention-to-treat (ITT) approach.

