hypothesis and 0.88 under the alternative hypothesis. The proportion is 0.66. If it is assumed that 10% of patients will withdraw consent or be lost to follow up, then 63 patients will need to be enrolled into this trial.

**Treatment Plan:** All participants will receive SOC endocrine therapy (fulvestrant or AIs) and PI3K inhibition (alpelisib). Participants will receive benralizumab 30mg subcutaneously on day -1. All participants will be monitored at regular visits for the duration of the trial. After 4 weeks, patients will be followed for safety at 90 days and disease progression for 1 year.

**Estimated Time to Completion:** 1 years.

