## 10.0 TREATMENT/INTERVENTION PLAN

Patients will receive fulvestrant or AIs 500 mg IM on days 1, 15, 29 and once monthly thereafter. Alpelisib 300mg by mouth once daily will be initiated with the first fulvestrant or AIs dose (day 1). Patients will continue alpelisib and endocrine therapy until disease progression or unacceptable toxicity as determined by their treating clinician.

Patients will receive benralizumab on day -1 to -7 of alpelisib initiation. Skin tape strips and research blood will be collected prior to alpelisib initiation.

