### 12.1 End of Study

The end of study will occur when all patients have been followed for 1 year or death, withdrawal of consent, or are lost to follow-up.

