### General Statistical Plan

There will be one analysis population for the current study. The modified intent to treat (ITT) population will be all patients regardless of treatment compliance for whom investigators were able to obtain a 4-week efficacy assessment. The safety population will be patients who received at least one dose of study drug or the standard of care, regardless of any efficacy assessments. All efficacy analyses will be based on the modified ITT population. Patient, clinical and safety data as well as primary, secondary and exploratory endpoints will initially be presented descriptively as means, medians, or proportions with appropriate measures of variance (i.e. range, SD, 95%CI). The primary endpoint,  $\geq$  grade 2 rash versus  $<$  grade 2 rash will be evaluated using generalized linear models (GLIM), with a logit link function and a Bernoulli distribution. A group\*time interaction will be included to assess the difference in the outcome measure at the specific study time points. Differences in the frequency of grade 0/1 rash overall all study visits (days 14, 28 and 90) will be assessed using mixed models for repeated measures as a secondary analysis.

The total number of dose reductions and delays between study groups over the trial period will be compared using Poisson regression analysis. The absolute difference in the FACT-B and PRO-CTCAE scores from day 1 to 14 and 28 between groups will be also be evaluated using repeated measures mixed models. The cumulative dose of corticosteroid use between

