the Benralizumab group over the study period will be compared using the Wilcoxon Rank Sum test. Time to the development of grade 1 or 2 rash will be evaluated using Kaplan-Meier time to event curves and assessed using the log rank test and Cox proportional hazards regression analysis. The Yates corrected chi square test will be used to compare the frequency of non-skin alpelisib related adverse events between groups, as well as 6 and 12 month ORR and PFS. Differences between the Benralizumab group on IL-5 inhibition and antihistamines and non-skin alpelisib related adverse events will be evaluated using linear mixed models. Changes in inflammatory biomarkers in skin and related to rash and all other exploratory endpoints will only be evaluated graphically with descriptive statistics. Given the exploratory nature of the current trial, there will be no adjustments for multiplicity. All the statistical analyses will be performed using SAS® Version 9.4 or higher. De-identified data will be shared via MSK secured e-mail quarterly to Augmentium Pharma Consulting for statistical analysis.

Patients may be removed from the study for various reasons as outlined in section 12.0 of the protocol. Descriptive statistics will be reported separately for patients removed from the study, including a summary of reasons for removal, their median duration in the study and range, median, range, and the distribution of rash grades at all follow-up times prior to their removal from the study.

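### Section 12.0 does not separate stopping treatment from leaving the study, so patients with toxicity could miss the Day 90 assessments

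*Combined protocol and SAP*

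**What the plan says.** Section 12.0 is headed as criteria for removal from the study. Criterion 1 is "> 2 consecutive weeks of a delay in treatment due to toxicities". Criteria 2 and 3 are progression and unacceptable toxicity. They stand in the same list as withdrawal of consent and death. The section expects few removals because 4-week PFS in this population exceeds 90%. It keeps patients evaluable for the primary endpoint if that endpoint is obtained, including those with a rash event before 4 weeks.

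Other sections bear on what happens next:

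- Section 10.0 uses progression and unacceptable toxicity as reasons to stop drug: "Patients will continue alpelisib and endocrine therapy until disease progression or unacceptable toxicity as determined by their treating clinician".
- Section 12.1 ends the study "when all patients have been followed for 1 year or death, withdrawal of consent, or are lost to follow-up".
- Section 1.0 plans: "After 4 weeks, patients will be followed for safety at 90 days and disease progression for 1 year".
- Table 9 schedules a skin exam, vital signs, concomitant medications, questionnaires and adverse event evaluation at Day 90, and a chart review at Day 365.
- Section 14.0 plans a secondary mixed-model analysis: "Differences in the frequency of grade 0/1 rash overall all study visits (days 14, 28 and 90"). For patients removed, it reports reasons, time in study and "the distribution of rash grades at all follow-up times prior to their removal from the study".

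**The concern.** The plan never says whether a patient who meets criterion 1, 2 or 3 stops alpelisib only or also stops attending visits. The heading of 12.0 and the section 14.0 summary both point to the second. Sites could reasonably act on that, and different sites could act differently.

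At stake is Day 90. Patients removed for toxicity are the ones most likely to have rash, other adverse events or steroid use, so their absence is informative. Removal for progression mainly reduces the number with Day 90 data. Removal also protects nobody from further study drug: benralizumab is a single injection given before alpelisib starts (sections 5.0 and 10.0), so leaving the study during an alpelisib hold loses data without sparing exposure.

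**Working it through.** **1. The texts side by side.** Three of the events in 12.0 (long toxicity hold, unacceptable toxicity, progression) are absent from the 12.1 list of reasons for incomplete follow-up (death, withdrawal of consent, loss to follow-up). Two of them are treatment-stopping events in 10.0. Neither section 1.0 nor Table 9 limits Day 90 to patients still on alpelisib. No sentence provides for visits after removal, and none says that they stop.

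**2. When criterion 1 takes effect.** A hold whose first day is Day d exceeds 14 days on Day d + 14. It removes the patient before a visit on Day v if d + 14 < v, that is d ≤ v − 15. Section 11.0 sets the visits at "day 14, and day 28 with a +/- 7 day window".

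| Visit day v | Latest start of hold, v − 15 |
|---|---|
| 21 (earliest Day 28 visit) | Day 6 |
| 28 | Day 13 |
| 35 (latest Day 28 visit) | Day 20 |
| 90 | Day 75 |

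A hold for non-rash toxicity starting by about Day 13 can therefore lose the Day 28 assessment. The modified ITT population in 14.0 requires a 4-week efficacy assessment, so that patient would leave the primary analysis.

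**3. How many are removed for toxicity.** This cannot be derived. Long holds are plausible: section 15.0 reports grade 3 hyperglycemia in 33%, and Table 3 requires interruption and allows up to 21 days on antidiabetic treatment before permanent discontinuation. No section gives the share of holds longer than 14 days. The 25% adverse event discontinuation rate in section 3.3 covers a whole phase 3 trial and counts permanent stops, not holds, so it does not supply the figure.

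**4. How many progress or die.** Inputs: median PFS of 11 months (section 3.3), N = 63. Assumption: constant hazard. The median in days is 11 × 30.44 = 334.8, and PFS(t) = 0.5^(t/334.8).

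- Day 28: 0.5^(28/334.8) = 0.944, so 5.6% have an event (0.056 × 63 ≈ 3.5). This agrees with the plan's statement that 4-week PFS exceeds 90%.
- Day 90: 0.5^(90/334.8) = 0.830, so 17.0% have an event (0.170 × 63 ≈ 10.7).
- Between Day 28 and Day 90: 0.944 − 0.830 = 0.114 (0.114 × 63 ≈ 7.2).

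The plan's reassurance is thus right for 4 weeks but does not reach Day 90, and it says nothing about toxicity.

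**5. Illustration only.** If toxicity removed an assumed 5%, 10% or 15% by Day 90, independently of progression, the total removed would be 1 − 0.830 × 0.95 = 21%, 1 − 0.830 × 0.90 = 25% or 1 − 0.830 × 0.85 = 29%, about 13, 16 or 19 of 63.

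**The case against.** **It is only an ambiguity.** Section 12.1 defines when the study ends, not each patient's follow-up, and no sentence says that visits stop. Reading 12.0 as off-treatment criteria would reconcile the text. This stands against calling the two sections flatly contradictory, as a reader might. It does not remove the problem, because the heading of 12.0 and the pre-removal rash summary in 14.0 favour the other reading.

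**Little depends on Day 90.** Section 3.4 says 90% of rash develops within 4 weeks, and a mixed model still uses a removed patient's Day 14 and Day 28 grades. Both points stand for rash onset. But removal for a non-rash toxicity is not explained by earlier rash grades. Other events come later: section 15.0 gives a median onset of 46 days for grade 2 or 3 diarrhea, and non-skin adverse events are a secondary objective. The planned quality-of-life comparison is "The absolute difference in the FACT-B and PRO-CTCAE scores from day 1 to 14 and 28 between groups", so it is exposed only to the limited Day 28 loss.

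**Safety reporting continues.** Sections 15.1 and 15.2 require SAE reporting for 30 days after the last treatment and reporting of certain treatment-related events after that. Treated patients stay in the safety population. This stands, so a reader should not infer that safety data are lost wholesale. The exposure is mainly non-serious events, skin findings and concomitant medications at one visit.

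**A larger progression figure is tempting.** Extending the 90% four-week floor to Day 90 gives 1 − 0.90^(90/28) = 29%. That is not a usable upper limit. Under the same constant hazard it implies a median PFS of 28 × ln 0.5 / ln 0.9 = 184 days, about 6 months, against the 11 months in section 3.3.

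**Conclusion.** The point holds as a modest design flaw that is cheap to correct. As written, 12.0 ties leaving the study to toxicity and progression. Followed literally, it loses Day 90 data selectively from patients with toxicity.

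The size is only partly known. The toxicity count is not derivable. For progression or death it is about 17% by Day 90, about 11 of 63 and about 7 of them after Day 28. This assumes a constant hazard and similarity to the phase 3 population, includes deaths whose Day 90 data cannot be recovered, and depends on when standard-of-care imaging detects progression. The direction of any bias in Day 90 rash cannot be settled: these patients are more prone to rash, but many would be off alpelisib by then.

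A reader might infer that the primary result is compromised. The documents do not support that. The exposure at 4 weeks is limited to removals before the Day 28 visit, and a rash event before 4 weeks keeps the patient evaluable.

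**What to change.** 1. Retitle criteria 1 to 3 of section 12.0 as criteria for stopping protocol treatment. Keep the 2-week limit there as a treatment-stopping rule: the dose tables set no maximum hold for grade 3 rash, diarrhea or other grade 3 toxicity, so it is the only general cap. Say which rule governs where Table 3 allows up to 21 days.
2. Keep removal from the study for withdrawal of consent, death, loss to follow-up, and illness or investigator judgement that further participation is not possible or not safe (criteria 4 and 7).
3. State that patients who stop alpelisib keep the Day 28 and Day 90 skin, adverse event, concomitant-medication and questionnaire assessments and the Day 365 chart review.
4. In section 14.0, report these patients' rash grades through Day 90, flag each assessment as on or off alpelisib, and add a sensitivity analysis restricted to on-alpelisib assessments. Without this, off-drug grades could flatter rash control.

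The cost is a protocol amendment and a few off-treatment visits that Table 9 already schedules. The downside is that some Day 90 rash grades will be recorded off alpelisib, which step 4 handles.

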## 1.0 PROTOCOL SUMMARY AND/OR SCHEMA

This is a multi-center, open-label, phase 2 trial testing the efficacy and safety of 2 interventions that target rash during PI3K inhibitor therapy in postmenopausal women and men with histologically-confirmed, hormone receptor (HR)-positive, HER2-negative, PIK3CA mutant metastatic breast cancer (MBC). A total of 63 patients will be enrolled into one arm: benralizumab 30mg in combination with standard of care (SOC) endocrine therapy (fulvestrant or AIs or aromatase inhibitors (AIs)) and PI3K inhibition (alpelisib). A total of 43 patients will be enrolled at MSKCC and a total of 20 patients will be enrolled at the participating external institutions (10 patients at Stanford University and 10 patients at Dana Farber Cancer Institute). The primary endpoint is the proportion of patients with grade  $\leq 1$  rash rate at 4 weeks.

**Patient Population:** The primary study population will be postmenopausal women and men with histologically-confirmed, HR-positive, HER2-negative, *PIK3CA* mutant MBC who have received no more than 2 lines of endocrine-based therapy in the metastatic setting.

**Design:** A multi-center, open-label, phase 2 trial testing the efficacy and safety of one interventions (one anti IL-5 receptor antibody and one antihistamine) that target the maculopapular rash during PI3K inhibitor therapy in patients with HR-positive, HER2-negative, *PIK3CA* mutant MBC receiving first or second line therapy. Study participants (n=112) will enrolled to one arm: benralizumab (anti-IL5ra) in combination with SOC endocrine therapy (fulvestrant or AIs) and PI3K inhibition (alpelisib). The primary endpoint is the grade  $\leq 1$  rash rate at 4 weeks. The study size is determined to compare the grade  $\leq 1$  rash rate at four weeks with historical controls. It has been reported that approximately 34% of patients receiving alpelisib will develop  $\geq$  grade 2 rash within the first 30 days. The corollary is that 66% of historical controls will have grade  $\leq 1$  rash within the first 30 days. An increase in rash control to approximately 88% is deemed to be clinically meaningful with the investigational agent under investigation (IL5r antibody). A sample size of 57 patients per group will achieve an 80% power to detect an odds ratio of 4.0 with respect to the primary endpoint. The proportion in the experimental group is assumed to be 0.66 under the null

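### Sections 12.0 and 14.0 define evaluability for the primary rash endpoint differently and give no rule for patients removed before Day 28, so the denominator can depend on outcome, in either direction

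*Combined protocol and SAP*

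**What the plan says.** Section 12.0 (Criteria for Removal from Study) lists nine grounds for removal. Item 5 is "Major protocol violation that would render the patient inevaluable for efficacy" and item 6 is "Repeated non-compliance by the patient with protocol requirements". The terms major, repeated and inevaluable are not defined. Below the list, the same section adds: "All participants for whom we are able to obtain the 4 week primary endpoint (had rash event prior to 4 weeks) will be considered evaluable", under an intention-to-treat approach. It also says that removals are not expected to be frequent.

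Section 14.0 (General Statistical Plan) defines the modified ITT population as "all patients regardless of treatment compliance for whom investigators were able to obtain a 4-week efficacy assessment", and states: "All efficacy analyses will be based on the modified ITT population". On removed patients it says: "Descriptive statistics will be reported separately for patients removed from the study". That report includes the "distribution of rash grades at all follow-up times prior to their removal from the study". It does not say whether these patients are in the primary analysis.

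Section 13.1 defines success as a rash grade of 1 or less at 4 weeks. Table 9 schedules a skin exam at Day 14±7 and Day 28±7. On blinding, Section 1.0 says: "This is a multi-center, open-label, phase 2 trial".

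**The concern.** Item 5 assumes that a violation can make a patient inevaluable. Section 14.0 recognises only one ground for leaving the efficacy set, the absence of a 4-week assessment. The sentence under the removal list gives a third rule, under which an early rash event is enough. Nothing says which rule prevails.

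Removal can produce the missing assessment. No text requires the Day 28 exam once a patient is off study, and no text scores a missing week-4 grade. Removal is decided after treatment has started, at visits where rash is also seen and with no blinding. If removal is related to rash, the set of patients analysed is selected on the outcome. With no concurrent arm to carry the same selection, any distortion passes straight into the comparison with the historical 0.66.

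The same gap applies to the toxicity-related exits (items 1, 3 and 7), which lie closer to rash than items 5 and 6 do.

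**Working it through.** **Step 1. The rules side by side.** Take patients removed early who have no later skin exam, and one who stays to the Day 28 visit.

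| Patient | Section 12.0 | Section 14.0 |
|---|---|---|
| Grade ≥2 rash recorded, then removed | Evaluable, by the sentence under the list | Out: no 4-week assessment |
| No rash, then removed | Not evaluable: no endpoint and no rash event | Out |
| Grade 1 rash, then removed | Unclear: the rash event carries no grade | Out |
| Item 5 violation, 4-week assessment obtained | Inevaluable by item 5, evaluable by the sentence below it | In |

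Under 12.0, early failures stay and rash-free early removals drop out, so the success rate is pushed down. Under 14.0, both drop out, and the rate is pushed up if failures are removed more often than successes.

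**Step 2. The plan's own figure.** Section 14.0 gives 57 patients for 80% power, 0.66 against 0.88, from a two-sample proportions test. No alpha is stated. With two-sided 0.05 and pooled variance (mean proportion 0.77):

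n = [1.96·√(2·0.77·0.23) + 0.842·√(0.66·0.34 + 0.88·0.12)]² / 0.22² = 56.2, rounded up to 57. Then 57 × 1.1 = 62.7, rounded to 63.

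This reproduces the plan, so one-sided 0.025 is a reasonable assumption for what follows. The plan states no one-sample decision rule; an exact binomial test against 0.66 is assumed.

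**Step 3. Reference case.** With all 63 analysed, the smallest count with exact tail probability at or below 0.025 is 50 of 63. Type I error is 0.015, and power at 0.88 is 0.984.

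**Step 4. Loss related to outcome.** Let f be the fraction of failures lost and s the fraction of successes lost. The expected success rate among those analysed is

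p(1−s) / [p(1−s) + (1−p)(1−f)], with p = 0.66.

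For f = 0.20 and s = 0 this is 0.66 / (0.66 + 0.34·0.80) = 0.66/0.932 = 0.708. Type I error sums the exact binomial probabilities, with the critical value reset for each analysed n.

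| Failures lost | Successes lost | Expected rate | Type I error |
|---|---|---|---|
| 0 | 0 | 66.0% | 1.5% |
| 10% | 0 | 68.3% | 4.2% |
| 20% | 0 | 70.8% | 9.1% |
| 30% | 0 | 73.5% | 18.2% |
| 20% | 5% | 69.7% | 6.5% |
| 10% | 10% | 66.0% | 1.8% |
| 0 | 10% | 63.6% | 0.7% |

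Expected failures are 63 × 0.34 = 21.4, so the failure-only rows lose about 2, 4 and 6 patients. Six is also the whole attrition allowance (63 − 57).

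**Step 5. Extremes with exactly six lost.** If all six are failures, the expected rate under the null is 41.58/57 = 72.9% and type I error is 0.22. If all six are rash-free, the rate is (41.58 − 6)/57 = 62.4% under the null and (55.44 − 6)/57 = 86.7% under the alternative.

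**The case against.** A reader might infer that unblinded investigators can take rash failures out of the denominator and so inflate the result. The documents do not support that as a general statement. The sentence in 12.0 about a rash event before 4 weeks keeps known early failures in. Active rash at a visit is to be graded and photographed by dermatology (Section 11.0), so it should be on record before any removal. An exam from Day 21 falls within the Day 28 window. If 12.0 governs, the patients lost are mainly those without rash, and the bias runs against benralizumab.

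A reader might also infer that 14.0 keeps everyone, so that items 5 and 6 cannot coexist with it. That goes too far. Section 14.0 requires a 4-week assessment, and items 5 and 6 govern leaving the study. A removed patient whose endpoint was obtained can still be analysed.

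The type I error figures depend on assumed removal rates, an assumed direction and an assumed test. That rash causes non-compliance is plausible but not documented, benralizumab is a single injection given before alpelisib starts, and removals are expected to be infrequent. Loss unrelated to outcome does almost no harm (1.8%).

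All of this stands, and it limits the claim. It does not remove the gap. Section 14.0 does not repeat the rash-event clause, 13.1 fixes the endpoint at 4 weeks, the clause gives no grade, and item 5 still declares some patients inevaluable. Under either section the denominator can depend on outcome.

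**Conclusion.** The concern holds as a conflict between two definitions of evaluability, combined with the absence of any rule for early removal or a missing week-4 grade. The direction of bias is not determined by the documents: upward if 14.0 governs and failures are removed more often, downward if the 12.0 sentence governs.

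Type I error ranges from 0.7% (10% of successes lost) to about 18% (30% of failures lost), against 1.5% with no loss. This rests on n = 63, a true rate of 0.66 and an exact one-sided 0.025 test. The documents give no removal counts, so these are scenarios and not estimates; 18% in particular requires losses equal to the whole attrition allowance, all of them failures.

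A reader might infer that deleting items 5 and 6 would be enough. It would not: a patient who misses the Day 28 visit would still fall outside the modified ITT set. This is a cheap improvement, best made before rash data are reviewed.

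**What to change.** Amend 12.0 and 14.0 together:

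1. Take the reference to efficacy inevaluability out of item 5, and record items 5 and 6 as protocol deviations that do not affect the analysis set.
2. Still perform the Day 28 skin exam already in Table 9 for patients removed for any reason who have not withdrawn consent.
3. Use one primary denominator, all treated patients, in both sections. Say what treated means, since benralizumab precedes alpelisib.
4. Count a grade 2 or worse rash recorded before removal as a failure.
5. State one rule for a missing week-4 grade, with a sensitivity analysis under a different rule.
6. Make any per-protocol analysis secondary, with the list of major violations fixed before rash data are reviewed.

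The cost is short amendment text, a little more analysis and no new type of visit. The estimate may be less favourable. The choice under point 5 matters for power. If six patients had no grade and all counted as failures, reaching 50 of 63 would need at least 50 successes among 57; at 0.88 that has probability about 0.62, against 0.98 with nothing missing. Keeping the Day 28 exam limits that loss. Treatment decisions are unaffected.
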